#### 6.4 Data Summarization and Presentation

SAS software (version 9.4, Cary, North Carolina) will be used for all data presentation and summarization including statistical analyses, summary tables, graphs, and data listings.

All data will be presented in listings, ordered by subject, study visit, IP, and time point, unless otherwise specified.

PK data will be summarized for the PK population. In addition, PK data will also be summarized for the randomized population if there is at least a difference of 1 subject between the populations.

The 95% confidence interval (CI) of the arithmetic mean, median, first and third quartiles, minimum, maximum; for log-normal data, the geometric mean, geometric coefficient of variation (CV), and 95% CI of the geometric mean will be presented instead of arithmetic mean, SD, and 95% CI of the arithmetic mean, respectively.

For log normally distributed endpoints (Cmax, AUC0-24h and AUC0-Tmax), geometric mean, geometric CV, and confidence interval will be presented additionally.

Measured plasma nicotine concentrations and derived PK parameters will be summarized with descriptive statistics including number of subjects (n), number and percent of subjects with missing data (Missing, n (%)), arithmetic mean (Mean), arithmetic standard deviation (SD), 95% confidence interval (95%CI), minimum, first quartile (Q1), median, third quartile (Q3), and maximum. Summaries will be further stratified by Sex.

For log normally distributed endpoints (Cmax, AUC0-24h and AUC0-Tmax), geometric mean (Geo. Mean), 95% geometric confidence interval (Geo. 95% CI) and geometric CV (Geo. CV%) will be presented additionally.

For observed plasma nicotine concentrations, the number and percent of values below LLOQ (BLQ, n(%)) or above ULOQ (ALQ, n(%)) will be presented in each summary table.

Ordinal categorical data (e.g., Tmax) will be summarized by number of subjects (n), number and percent of subjects with missing data, median, first and third quartiles, and minimum and maximum.

All PK analyses and summaries will be performed by product.

The analytical data will be presented in the tables/listings to the same precision as received from the analytical laboratory.

The level of precision will be presented as follows: minimum/maximum in the same precision as in the database, mean/median in one more precision level than minimum/maximum, SD in

Philip Morris Products S.A.  
 THS Induction device and regular or menthol sticks, P1-PK-12  
 [REDACTED] CA39924

---

one more precision level than mean/median, and n will be presented as an integer. Percentages will be presented as an integer.

Where individual data points are missing because of dropouts or other reasons, the data will be summarized based on reduced denominators. Missing PK data will be treated as missing and no data imputation will be conducted.

Mean and individual plasma nicotine concentrations will be presented graphically (linear and semi-log plots; linear plots will be presented with and without SD).

## 6.5 Statistical Analysis of Pharmacokinetic Parameters

### 6.5.1 Main Analysis

A mixed model analysis of variance (ANOVA) will be conducted on Cmax, AUC0-24h, and AUC0-Tmax endpoints in the natural logarithmic scale.

The model will include terms for sequence, period, product as fixed effects and subject as a categorical random effect modeling the within subject correlations.

The ANOVA analysis could be performed using the following SAS code:

```
PROC MIXED data=<> method=REML;
class subject sequence period product;
model log(parameter) = sequence period product/ddf=KR;
repeated product / subject=subject type=csh;
lsmeans product / pdiff=control("CIG") cl alpha=0.05;
RUN;
```

The results of this analysis for each of are presented in terms of geometric least square ratios and 95% confidence intervals for each THS / CIG ratio.

This approach is consistent with the guidelines in the European Medicines Agency's guidelines for bioequivalence investigations and FDA's Center for Drug Evaluation and Research.

The analysis of Tmax will be performed by conducting a Wilcoxon signed rank test and calculating the median Tmax for each product along with the Hodges-Lehmann estimate of the median difference between products, and the related 95% CI.

This analysis could be performed using the following SAS code:

```
PROC NPAR1WAY hl(refclass=<>) alpha=.05 data=<> hl;
class TRT;
var AVAL;
ods output HodgesLehmann=HodgesLehmann;
RUN;
```

Philip Morris Products S.A.  
 THS Induction device and regular or menthol sticks, P1-PK-12  
 [REDACTED] CA39924

---

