12.1.4 Significance Level for Inferential Analysis

No significance level will be used. All confidence intervals will be computed at 95%.

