### 3. STUDY DESIGN

This study is designed to meet the objectives outlined in [Section 2](#).

This is a single-center, randomized, controlled, open-label, cross-over study in healthy subjects. The study will be conducted with 3 periods and 6 sequences in a cross-over design.

Philip Morris Products S.A.  
 THS Induction device and regular or menthol sticks, P1-PK-12  
 CA39924

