### Figure 1 Study Design

Abbreviations: CIG = combustible cigarette; P1M = menthol taste; P1R = regular taste

A Screening visit will be conducted within 27 days (Day -28 to Day -2) prior to admission (on Baseline Day -1) to the investigational site (Figure 1) to check and document the eligibility of the subjects. Investigational site staff will demonstrate the THS (without product use) during the Screening visit. The brand of subjects' cigarettes will be recorded.

Qualified subjects will return to the investigational site for Baseline on Day -1. Subjects will have fasted for at least 6 hours prior to the safety laboratory assessments. After confirmation of eligibility, subjects can be randomized. All subjects who will not be randomized will be documented as screen failures.

Thirty subjects will be randomized to one of 6 possible full crossover sequences of IP use (THS with either regular or menthol stick, and CIG) on Day 1 to Day 3 (see Figure 1). After admission on Baseline Day -1 in the morning, nicotine wash-out will start, and the use of any other tobacco and/or nicotine containing products (TNP) different from the IP assigned for use on Day 1 to Day 3, will not be allowed. Use of TNP will not be restricted after the subject has been discharged from the investigational site on Day 3.

Philip Morris Products S.A.  
THS Induction device and regular or menthol sticks, P1-PK-12  
[REDACTED] CA39924

---

On Day 1 to Day 3, after at least 23 hours of abstinence from any TNP on Day 1, and after at least 24 hours of former IP use on Day 2 and Day 3 (nicotine wash-out), subjects will smoke a single CIG or perform a single use of a THS either with a regular or a menthol stick, according to randomized product use sequence.

The start of IP use will be defined as T0. T0 on Day 1 to Day 3 should be at approximately the same time in the morning. Venous blood samples will be obtained according to the standard operating procedures (SOPs) at the investigational site. Subjects will report their cigarette craving, IP liking, and intention to use again by performing VAS assessments.

After Discharge on Day 3 or after Early termination following product exposure, the subjects will enter a 3-day Safety follow-up (SFU) period during which AE/SAEs reported by the subjects will be collected and the follow-up of AEs/SAEs will be conducted, concluded per a telephone contact by the investigational site on the last day of the SFU period.

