**Table ITPStat2**

**Statistical Comparisons of Plasma Nicotine Pharmacokinetic Parameter Tmax for THS and CIG (PK Population)**

Comparison	Parameter	Difference <X> - <Y>		
		Median	95% Confidence Interval	p-value
P1R vs CIG	Tmax	X.XX	X.XX-X.XX	X.XXXX
P1M vs CIG	Tmax	X.XX	X.XX-X.XX	X.XXXX
P1R: <> P1M: <> CIG: <>				
The difference between products (product effect) and the 95% confidence interval for the difference was calculated using Hedges-Lehmann estimator.				
Source: Table 14.2.1.8				

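### The Tmax code is an unpaired two-sample procedure in a crossover study, so its Hodges-Lehmann interval ignores pairing and does not match the signed rank test named in the text

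*SAP*

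**What the plan says.** SAP section 3 describes the design: "The study will be conducted with 3 periods and 6 sequences in a cross-over design". The text under its Figure 1 adds that "Thirty subjects will be randomized to one of 6 possible full crossover sequences of IP use". Each subject who completes therefore contributes one Tmax value per product.

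For the analysis, SAP 6.5.1 states that "The analysis of Tmax will be performed by conducting a Wilcoxon signed rank test", and that it will be reported with the median Tmax for each product and the "Hodges-Lehmann estimate of the median difference between products, and the related 95% CI". The code is introduced with "This analysis could be performed using the following SAS code" and opens with "PROC NPAR1WAY hl(refclass=<>) alpha=.05 data=<> hl". It then names `TRT` as the class variable and `AVAL` as the analysis variable, and outputs the Hodges-Lehmann results. There is no subject identifier, difference variable, period or sequence.

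Protocol 12.4.1.4 has the same text and the same code. SAP section 9 reports that the analyses are aligned with the protocol, so the mismatch was carried across. Neither document contains paired code for Tmax. Table ITPStat2 in the SAP prints the median difference, its 95% interval and a p-value in one row for each of P1R versus CIG and P1M versus CIG.

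**The concern.** The signed rank test works on within-subject differences. PROC NPAR1WAY works on independent groups, and its Hodges-Lehmann option gives the median of all cross-group differences with limits from the rank-sum distribution. The text and the code therefore answer different statistical questions, and only the text fits the design. In the same SAP section the mixed model for Cmax and the AUCs is set up to model the correlation within subjects; only Tmax would lose it.

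A programmer who follows both parts literally would print a paired p-value next to an unpaired interval. In a study whose purpose is description, the estimate and its interval are the result, so an interval labelled 95% that covers about 99% is mislabelled. The precision that the crossover buys for this primary endpoint is also thrown away.

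**Working it through.** **Inputs from the documents.** There are 30 subjects in a full crossover, so up to 30 pairs per comparison. Intervals are two-sided 95%. Nominal early sampling times are 4, 6, 8, 10, 12, 15, 30 and 60 minutes. The plan gives no precision or power figure for Tmax, so there is none to reproduce. It also gives no Tmax standard deviation and no within-subject correlation ρ; the values below are assumptions.

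**Theory.** Let each product's Tmax have variance σ². The variance of the estimated shift is about 2σ²/n if the groups are treated as independent, and 2σ²(1−ρ)/n when pairing is used. This gives:

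- width ratio, unpaired to paired: 1/√(1−ρ)
- actual coverage of the unpaired interval: 2Φ(1.96/√(1−ρ)) − 1

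At ρ = 0, 0.3, 0.5 and 0.7 the ratio is 1.00, 1.20, 1.41 and 1.83, and the coverage is 95.0%, 98.1%, 99.4% and 99.97%.

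**How the two intervals are formed at n = 30.**

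- Unpaired: sort the 30 × 30 = 900 cross-differences and cut at 450 − 1.96 × √(900 × 61/12) = 450 − 132.6, about the 317th from each end.
- Paired: sort the 30 × 31/2 = 465 Walsh averages and cut at 232.5 − 1.96 × √(30 × 31 × 61/24) = 232.5 − 95.3, about the 137th from each end.

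**Simulation 1.** Normal data, true shift 0.5 SD, 4,000 runs per ρ:

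| ρ | Unpaired coverage | Paired coverage | Width ratio | Unpaired excludes 0 | Paired excludes 0 |
|---|---|---|---|---|---|
| 0 | 95.1% | 94.9% | 0.99 | 46% | 45% |
| 0.3 | 97.8% | 95.3% | 1.18 | 46% | 58% |
| 0.5 | 99.2% | 94.7% | 1.39 | 44% | 73% |
| 0.7 | 99.9% | 95.4% | 1.78 | 44% | 91% |

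The mean point estimates were 0.497 to 0.498 unpaired and 0.495 to 0.499 paired, so the shift itself is not biased under these assumptions.

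**Simulation 2.** Lognormal Tmax, assumed median 8 minutes and log-SD 0.35. The width ratio was about 0.93, 1.12, 1.31, 1.69 and 2.04 at ρ = 0, 0.3, 0.5, 0.7 and 0.8. For an assumed true shift of 1.5 minutes, the paired interval excluded zero in about 75% of runs and the unpaired in 54% at ρ = 0.5; at ρ = 0.7 the figures were 93% and 55%. In the same scenario the signed rank p-value (judged at 0.05) and the unpaired interval disagreed about zero in about 24% of runs at ρ = 0.5 and 37% at ρ = 0.7.

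**Simulation 3.** Tmax rounded to the nominal sampling times, 2,000 runs, assumed median 8 minutes and log-SD 0.4. With no true difference the width ratio was 0.95, 1.14, 1.39 and 1.85 at ρ = 0, 0.3, 0.5 and 0.7. Ties make both intervals conservative: coverage was 98.6% to 99.8% paired and 99.7% to 100% unpaired. With a shift of 0.25 on the log scale, the paired interval excluded zero in 64% of runs and the unpaired in 14% at ρ = 0.5.

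**The case against.** The governing sentence already specifies a paired test, and the code is offered only as something that could be used. It cannot run as it stands: the dataset and reference class are blank, the `hl` option appears twice, and `TRT` has three levels where a two-sample comparison needs two. A careful programmer might never follow it. This stands as a limit on certainty: the wrong interval appears only if the template is used. But the documents give no other instruction for the interval.

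The study is also descriptive. It has no hypothesis, success criterion or significance level, and the main estimand's summary measure covers only Cmax and the AUCs. No decision in the documents turns on the Tmax interval, the error is conservative when correlation is positive, and the by-product medians and ranges are untouched. All of that is right, and it bounds the consequence. It does not make the interval correct.

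The size rests on assumed values. With Simulation 2's assumptions at ρ = 0.5, the mean widths are about 2.9 and 2.2 minutes, a difference of (2.9 − 2.2)/2 = 0.35 minutes per side, which is small against a 2-minute sampling interval. On the sampling grid the paired interval does not hold exactly 95% either. Both points stand, so the percentages are illustrative. The direction survived on the grid.

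Finally, the paired analysis has a cost. A subject missing either product drops out of that comparison, although Protocol 12.4.1 treats missing periods as missing at random, and a simple paired analysis does not adjust for period. The existing code does not adjust for period either.

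**Conclusion.** The concern holds. The text prescribes a paired test, the design is paired, and the only code supplied is unpaired and cannot deliver the named test. If the code is followed and within-subject correlation is positive, the reported interval is too wide: about 1.1 to 1.8 times the paired width for ρ between 0.3 and 0.7, with coverage of about 98% to 99.9% when Tmax is treated as continuous. It would also sometimes contradict the p-value in the same row. At ρ = 0 there is little difference.

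These sizes depend on assumed distributions and correlations that the documents do not give. The damage is to the interval and to its agreement with the p-value, not to the point estimate. Because Tmax is a primary endpoint and the correction is simple, it should be made before the analysis is run.

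**What to change.** Replace the Tmax code in SAP 6.5.1, and correct Protocol 12.4.1.4 or record the change in SAP section 9. For each of P1R minus CIG and P1M minus CIG:

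1. Form the within-subject difference in Tmax.
2. Run the signed rank test on the differences, for example with PROC UNIVARIATE.
3. Report the one-sample Hodges-Lehmann estimate (the median of the Walsh averages) with the 95% interval obtained by inverting the same signed rank test.

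State three conventions alongside this: that a subject without Tmax for both products is left out of that comparison, with the number of pairs shown; how ties and zero differences are handled, since sampling times are discrete; and that period is not adjusted for, or how it is. When the tables are edited, shell CPStat2 should also be brought into line, because its column header shows a 90% interval while the analysis text and Table ITPStat2 specify 95%.

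The cost is a few lines of code and a short text correction, with no new data. The one trade-off is the loss of incomplete pairs.

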### 6.5.2 Sensitivity Analyses

In case of any uncorrected nicotine concentration at  $T_0$  [ $\mu\text{C}_0$ ] greater than 5% of their uncorrected maximum value, a sensitivity analysis of the PK endpoints will be performed similarly to the main analysis, whereby data of these subjects for this specific study day will be excluded from the analysis.

### 6.5.3 Supplementary Analysis

No supplementary analysis is foreseen.

## 6.6 Preliminary Data and Interim Analysis

[REDACTED] Biometrics will not perform preliminary or interim analyses.

## 7. PHARMACODYNAMIC EFFECTS (SUBJECTIVE EFFECTS)

### 7.1 Data Collection

On Day 1 to Day 3, cigarette craving, product liking, and intention to use the product again will be assessed using a VAS (a 100 mm unipolar scale going from “no craving” to “strong craving” for VAS Craving; a 100 mm bipolar scale going from “strong disliking” to “strong liking” for VAS Liking; and a 100 mm bipolar scale going from “very unlikely” to “very likely” for VAS Intention to Use Again) at the following time points in relation to  $T_0$  with a time window as indicated in brackets:

#### Prior to $T_0$ (for VAS Craving assessment)

- $T_{v0}$ : within 15 minutes prior to  $T_0$

#### After $T_0$ (for VAS Craving assessment)

- $T_{v1}$  after 4 minutes ( $\pm 2$  minutes)
- $T_{v2}$  after 10 minutes ( $\pm 2$  minutes)
- $T_{v3}$  after 15 minutes ( $\pm 2$  minutes)
- $T_{v4}$  after 30 minutes ( $\pm 2$  minutes)
- $T_{v5}$  after 10 hours ( $\pm 5$  minutes)

#### After $T_0$ (for VAS Liking and VAS Intention to Use Again assessments)

- $T_{v3}$  after 15 minutes ( $\pm 1$  minute)

### 7.2 Data Summarization

Descriptive statistics (n, mean, SD, CV%, SEM, minimum, Q1, median, Q3, maximum, and 95% CI of mean) for VAS Craving assessment, VAS Liking assessment, and VAS

Philip Morris Products S.A.  
THS Induction device and regular or menthol sticks, P1-PK-12  
[REDACTED] CA39924

---

Intention to Use Again assessment will be provided by IP and assessment time point, as applicable. Change from baseline (pre-product use) for VAS Craving score will be summarized by IP and assessment time point. Individual responses will be listed. Summaries will be further stratified by sex.

PD data will be summarized for the PK population. In addition, PD data will also be summarized for the randomized population if there is at least a difference of 1 subject between the populations.

## 8. SAFETY

All relevant case report form (CRF) data will be listed by subject and chronologically by assessment time point. This will include rechecks, unscheduled, and early termination assessments.

Applicable continuous variables will be summarized using n, mean, SD, minimum, median, and maximum.

The level of precision will be presented as follows: minimum/maximum in the same precision as in the database, mean/median in one more precision level than minimum/maximum, SD in one more precision level than mean/median, and n will be presented as an integer. Percentages will be presented as an integer.

Where individual data points are missing because of dropouts or other reasons, the data will be summarized based on reduced denominators.

Baseline will be the result closest and prior to the product use in the respective period unless otherwise stated. Summaries for post-baseline time points will not include rechecks, unscheduled, or early termination measurements.

Tables summarizing safety data by assessment time point will only include summaries for baseline and post-baseline time points.

### 8.1 Subject Disposition

Subjects will be summarized by number of subjects screened, enrolled, enrolled and exposed to P1 product, randomized, completed, and discontinued the study with discontinuation reasons.

### 8.2 Protocol Deviations

Protocol deviations are captured by the clinical site and provided in the CSR in a similar format to that provided by the clinical site. Protocol deviations are not edited or processed in SAS®.

Philip Morris Products S.A.  
THS Induction device and regular or menthol sticks, P1-PK-12  
[REDACTED] CA39924

---

### **8.3 Demographics**

Descriptive statistics will be calculated overall for continuous variables (age, weight, height, and body mass index) and further stratified by sex.

Frequency counts will be provided for categorical variables (race, ethnicity, and sex) overall and further stratified by sex.

Demographic information and baseline characteristics (weight, height, and body mass index [BMI]) will be summarized for the safety and PK population. This summary will also be performed for the randomized population if there is at least a difference of 1 subject between the populations.

### **8.4 Tobacco/Nicotine-Containing Product Use History Questionnaire**

At the Screening Visit, subjects will be asked questions about their tobacco-and/or nicotine-containing product (TNP) use history. The questions will capture frequency and quantity of TNP use over the past 4 weeks, and number of continuous years of cigarette smoking.

Descriptive statistics will be calculated for continuous variables overall and further stratified by sex.

Frequency counts and percentage will be provided for categorical variables overall and further stratified by sex.

### **8.5 Usual Brand Cigarettes Documentation**

Subject's usual brand of cigarettes will be documented and frequency counts will be provided for categorical variables (substance, brand, brand style, flavor, and cigarette length) overall and further stratified by sex. Descriptive statistics will be presented for amount of use overall and further stratified by sex.

### **8.6 Fagerström Test for Nicotine Dependence (FTND)**

Potential nicotine dependence will be assessed at the Screening Visit using the FTND in its revised version as updated in 2012 ([Fagerström, K.O., 1978, Heatherton, T.F., et al., 1991](#)). The questionnaire consists of six questions, which have to be answered by the subject himself/herself. The total score obtained on the test permit the classification of nicotine dependence into three levels: Mild (0 to 3 points); Moderate (4 to 6 points); Severe (7-10 points) ([Fagerström, K., et al., 2012](#)).

Descriptive statistics will be calculated for FTND score. In addition, frequency counts will be provided for nicotine dependence levels (mild, moderate, and severe) overall and further stratified by sex.

Philip Morris Products S.A.  
THS Induction device and regular or menthol sticks, P1-PK-12  
[REDACTED] CA39924

---

## 8.7 Medical History

All Medical History and Concomitant Disease will be coded using the Medical Dictionary for Regulatory Activities (MedDRA®), Version 25.1 and listed by subject.

## 8.8 Adverse Events

All AEs occurring during this clinical trial will be coded using MedDRA®, Version 25.1.

All AEs captured in the database will be listed in by-subject data listings including verbatim term, coded term, product, severity, relationship to study product, and action; however, only product use-emergent AEs (PUEAEs) will be summarized. Adverse events after ICF and prior to the first product use on Day 1 and occurred during SFU period (after discharge from CRU to SFU visit) will be summarized separately under admission/SFU period.

A PUEAE is defined as an AE that is starting or worsening at the time of or after first study product administration. An AE that occurs during the washout period between study products is considered study product use emergent to the last study product given.

If the onset time of an AE is missing and the onset date is the same as the product administration date, the AE will be considered product use-emergent to the prior and current product. If the onset time of an AE is missing and the onset date does not fall on a product administration date, the AE will be considered product use-emergent for the last product administered. If the onset date of an AE is missing, the AE will be considered product use-emergent and attributed to each product on the study, unless the onset date is known to have occurred within or between specific product periods.

The number and percentage of subjects with AEs, SAEs will be tabulated by system organ class and preferred term. Summaries will also be presented for AEs leading to discontinuation, AEs leading to death, AEs by relatedness to product exposure, AEs by severity, and laboratory AEs. Tabulations will be performed for both the number of subjects experiencing an event and the number of events.

SAEs, if present, will also be listed. Applicable narratives will be included in the CSR.

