8.2 Collection and Reporting of Adverse Events

8.2.1 Collection of Information

AEs should be collected mainly via face-to-face interview with the subject by the use of consistent, open, non-directive questions from the investigator(s) or designee(s) (e.g., “How have you been feeling since you were last asked?”).

Any non-serious AE occurrence during the study must be documented in the subject's medical records in accordance with the Investigator's normal clinical practice and on the AE page of the CRF. SAEs that occur during the study must be documented in the subject's medical record, on the AE CRF, and on the SAE form for recording into safety database.

Information recorded for AEs/SAEs will include verbatim description, start and stop dates, seriousness, severity (intensity), causal relationship with IP and study procedures, expectedness, action taken with IP (e.g., reduced, not changed), other action taken (e.g., treatment administered, if led to the subject's discontinuation from the study), and outcome (e.g., resolved, stabilized).

Whenever a medically meaningful diagnosis is available to comprise a set of reported signs and/or symptoms, it should be preferentially provided as the AE or SAE term, rather than the individual signs and/or symptoms.

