8.2.2 Period of Collection

AEs (including SAEs) will be collected from the time of ICF signature until the individual EOS for each participant.

Any AEs which occur during the Screening period will be captured by the investigational site staff and assessed by the Investigator or designee(s) to establish relationship to study procedures.

During a 3-day SFU period new AEs/SAEs will be recorded and ongoing AEs/SAEs will be followed-up by the study site, as described in Section [8.2.6](#).

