### **4.2 Safety Population (SAF)**

The safety population is a subset of the screened population and consists of all subjects who give informed consent and have at least one safety assessment.

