**Table IAEQ Overall Product Use Emergent Adverse Events (Safety Population)**

Adverse Event	Admission (N=X)	Product Administration				SFU (N = X)
		P1R (N = X)	P1M (N-X)	CIG (N = X)	Overall (N = X)	
Number of Subjects With PUEAEs	XX (XX%)	XX (XX%)	XX (XX%)	XX (XX%)	XX (XX%)	XX (XX%)
Number of Subjects With SAEs	XX (XX%)	XX (XX%)	XX (XX%)	XX (XX%)	XX (XX%)	XX (XX%)
Number of Subjects With IP Events	XX (XX%)	XX (XX%)	XX (XX%)	XX (XX%)	XX (XX%)	XX (XX%)
Number of Subjects With AEs Leading to Discontinuation	XX (XX%)	XX (XX%)	XX (XX%)	XX (XX%)	XX (XX%)	XX (XX%)
Number of Subjects With AEs Leading to Death	XX (XX%)	XX (XX%)	XX (XX%)	XX (XX%)	XX (XX%)	XX (XX%)
Number of Subjects With AEs Related to IP	XX (XX%)	XX (XX%)	XX (XX%)	XX (XX%)	XX (XX%)	XX (XX%)

P1R: THS regular stick  
 P1M: THS menthol stick  
 CIG: Combustible cigarette  
 Although a subject may have had 2 or more adverse events, the subject is counted only once within a category. The same subject may appear in different categories.  
 PUEAEs = Product use-emergent adverse events; SAEs = Serious adverse events; IP = Investigational product  
 Admission = after ICF and prior to the product test on Day 1  
 SFU = after discharge from CRU to safety follow-up visit  
 Source: Table 14.3.1.1  
 Program: /CAXXXX/sas\_prg/stsas/intext/t\_ae.sas DDMMYYYY HH:MM

Philip Morris Products S.A.  
 THS Induction device and regular or menthol sticks, P1-PK-12  
 [REDACTED] CA39924

In-text Shell IAES will be in the following RFT format:

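### Read literally, the SAP's missing-onset-date rule charges an AE to all three products even if it ended before first use or the subject never used one of them

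*SAP*

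**What the plan says.** SAP 8.8 summarises product use-emergent AEs (PUEAEs) and gives this definition: "A PUEAE is defined as an AE that is starting or worsening at the time of or after first study product administration". It sends earlier events elsewhere: "Adverse events after ICF and prior to the first product use on Day 1" are reported under a separate admission/SFU heading. The AE table shells carry a column for them, with the footnote "Admission = after ICF and prior to the product test on Day 1" in Table IAEQ.

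The same section then sets a default for incomplete dates: "If the onset date of an AE is missing, the AE will be considered product use-emergent and attributed to each product on the study", with the exception "unless the onset date is known to have occurred within or between specific product periods".

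Four other statements bear on the point:

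- Protocol 8.2.2: "AEs (including SAEs) will be collected from the time of ICF signature until the individual EOS for each participant". Screening can be up to 27 days before Day -1 (protocol 9.1), so events before any product use are collected.
- Protocol 8.2.1: "Information recorded for AEs/SAEs will include verbatim description, start and stop dates".
- SAP 4.2: the safety population "consists of all subjects who give informed consent and have at least one safety assessment". Product use is not required.
- SAP 11.2, Tables 14.3.1.1 to 14.3.1.3: subject-level AE percentages are based on subjects who used the product.

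**The concern.** The exception covers an onset known to fall inside a product period or between two of them. An onset before the first period is neither. The rule also refers to every product in the study rather than every product the subject used. A programmer who codes that sentence as written would therefore enter an AE under P1R, P1M and CIG in two situations where the record rules that out: the stop date precedes first use, or the subject did not use one or more of the products.

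AE incidence is a secondary safety endpoint. The stake is a wrong count in the product columns, a matching gap in the Admission column and, for a subject who stopped early, a numerator containing someone outside the denominator.

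**Working it through.** The documents give no figure on this point, so there is nothing to reproduce. The check applies the SAP 8.8 rules to test cases and then sizes one misplaced AE.

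**Inputs.** Rules from SAP 8.8; three products and 30 randomized subjects (SAP 3); stop dates available (protocol 8.2.1); percentage base of subjects who used the product (SAP 11.2).

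**Step 1: two readings, onset date missing in every case.** Reading A applies the missing-date sentence alone, with its exception. Reading B applies the PUEAE definition and the Admission category first, and attributes only to products used.

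| Case | Reading A | Reading B |
|---|---|---|
| Timing unknown, all three products used | P1R, P1M, CIG | P1R, P1M, CIG |
| Onset known to be within or between periods | that period's product | that period's product |
| Stop date before first use | P1R, P1M, CIG | Admission |
| Only P1R used | P1R, P1M, CIG | P1R |
| No product used | P1R, P1M, CIG | no product |

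The readings agree when timing is truly unknown in a completer and when the existing exception applies. They differ in the last three rows.

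**Step 2: size in the subject-level tables.** One added subject contributes 1/N to a column:

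- N = 30: 1/30 = 3.3 percentage points
- N = 29: 1/29 = 3.4 points
- N = 28: 1/28 = 3.6 points

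This is an upper limit per AE, because the shells count a subject once per category. If the subject is already counted there, nothing is added.

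**Step 3: size in the event-count tables.** One AE × three product columns = 3 entries. The correct number of product entries is 0 for an event that ended before first use, and 1 for a subject who used only P1R.

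**Step 4: effect on product contrasts.**

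- *Subject used all three products.* With a and b subjects counted under two products, (a+1)/30 − (b+1)/30 = (a−b)/30, so the percentage-point difference does not change. A ratio moves toward 1. As an illustration with assumed counts, 2/30 against 4/30 is 0.50; after adding one to each, 3/30 against 5/30 is 0.60. The difference is 2/30 = 6.7 points both times.
- *Subject used only P1R.* If everyone else used all products, the P1M and CIG bases are 29, yet each numerator gains a subject who is not among those 29.

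**The case against.** The strongest reply is that SAP 8.8 has already answered the question. The PUEAE definition and the separate handling of earlier events come before the missing-date sentence. An event that ended before first use must have begun before it, so its position is known and the default has no work to do. A subject who used nothing cannot meet the definition at all. For an onset that is truly unknown, attribution to every product is a familiar conservative convention. The trigger is also rare: start and stop dates are required items, AEs are collected mainly by interview (protocol 8.2.1), and missing or unclear data go back to the investigator (protocol 11.1.1). The AE listing (Appendix 16.2.7.1) shows product, emergent flag, start and end, so a misplacement could be seen.

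Much of this stands. The definition-first reading is probably what was meant, the convention is reasonable where timing is unknown, and cases should be few.

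It does not remove the conflict. The SAP states no precedence, and an exception that names two situations can be read as complete. The sentence just before it also lacks a branch for time before use: an AE dated to screening with only its time missing goes to the last product administered, and there is none. It is therefore unsafe to rely on the definition overriding silently. The definition also does not help a subject who used one product and stopped, because an AE after that use can be emergent while two of the three attributions are still wrong.

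**Conclusion.** The concern holds as a conflict between rules in SAP 8.8 with no stated order. Under the literal reading, one affected AE adds up to 3.3 percentage points to a product column at N = 30 and three entries across the product columns of the event-count tables. This rests on the planned 30 subjects and on the subject not already being counted. The documents do not say how many AEs will lack an onset date; 0 to 3 is an assumption, and none is quite possible. It is a minor point.

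A reader might infer more, but the documents do not support it:

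- *That the SAP means to count events known to precede use.* Nothing says so, and its definition and Admission column point the other way.
- *That the apparent THS–CIG difference shrinks.* For a subject who used all three products the percentage-point difference is unchanged; only ratios move.
- *That product-related incidence rises.* Relatedness is a separate investigator judgment (protocol 8.2.4) with its own table rows. The date rule affects emergence only.
- *That missing dates cluster in events that began at home.* This is plausible but is not stated anywhere.

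**What to change.** Amend SAP 8.8 as follows:

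1. State that the PUEAE definition takes precedence over the rules for incomplete dates.
2. If the stop date or a partial onset date shows that the AE began before first product use, and it did not worsen after first use, count it under Admission.
3. Otherwise attribute an AE with a missing onset date only to products the subject actually used, and used before the AE ended. Keep the existing exception for an onset known to be within or between periods.

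The rule should rest on stop date, partial onset date and product-use records, all of which are available (Appendices 16.2.5.5 and 16.2.7.1). It should not depend on the visit at which the AE was first reported, because neither protocol 8.2.1 nor the AE listing shell names that item.

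The cost is two or three sentences and a small programming change, best made before the AE tables are programmed. No new data are needed.
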